3.3.2 Secondary Endpoints

- 1) A $\geq 75\%$ reduction in peak blood eosinophil count following the first dose of mepolizumab (as compared to the peak eosinophil count in the cycle preceding initiation of mepolizumab therapy).
- 2) Sustained reduction of eosinophilia after administration of mepolizumab (at Visit 8).

3.3.3 Exploratory Endpoints

- 1) Effect of mepolizumab on cycling of cells other than eosinophils (e.g., neutrophils and lymphocytes) following mepolizumab administration.

- 2) Effect of mepolizumab on markers of eosinophil activation and other biomarkers of disease activity in EAE, including whole blood transcriptomics, levels of eosinophil and neutrophil granule proteins, serum IgG and IgM levels, serum cytokine and chemokine levels, and serum tryptase levels.
- 3) Reduction of symptoms and severity of clinical symptoms of EAE on mepolizumab at doses of 500 mg and 300 mg.

4. Study Population

4.1 Rationale for Subject Selection

Subjects will be selected based on a confirmed diagnosis of EAE and demonstration of ongoing symptoms and cycling. Potential subjects whose peak eosinophil count is <1500/mm³ in the 3 months prior to enrollment will not be eligible.

4.2 Recruitment Plan

EAE is an extremely rare disorder. A maximum of 12 intention-to-treat subjects with EAE will be enrolled with a ceiling of 15 patients for subjects that drop out prior to receiving the first dose. Subjects who are withdrawn prior to receiving mepolizumab will be replaced. The anticipated recruitment period will be 2 years. Subjects will be recruited from those already enrolled on NIH protocol 94-I-0079 (“Eosinophil activation and function in parasitic infections and other conditions with increased tissue or blood eosinophilia in humans”). The NIH is a major referral center for HES, with >200 patients actively followed on protocol 94-I-0079, of which 12 are known to have EAE, and 1-2 new patients referred for evaluation of eosinophilia weekly.

4.3 Subject Inclusion Criteria

A subject will be eligible for participation in the study only if all of the following criteria apply:

- 1) The subject is male or female, aged 18 years or older.
- 2) The subject has a documented diagnosis of EAE.
- 3) The subject has symptoms of EAE in the cycle prior to screening, including but not limited to fever, swelling, hives or rashes, weight gain, muscle pain, and lymphadenopathy.
- 4) Cycling of eosinophils is ongoing as indicated by a peak AEC $\geq 1500/\text{mm}^3$ during at least one cycle in the prior 3 months.
- 5) If taking corticosteroids ≤ 40 mg daily, the subject is able and willing to stay on a stable dose for 6 weeks prior to screening.
- 6) The subject agrees to storage of study samples.

- 7) The subject is able to provide informed consent.
- 8) Females are eligible for this study if they are:
 - i. of non-childbearing potential (i.e., women who have had a hysterectomy or tubal ligation or are postmenopausal as defined by no menses in 1 year); OR
 - ii. of childbearing potential but willing to practice effective contraception or abstinence during administration of the study drug and for 100 days (5 terminal half-lives) after administration of the study drug.
 - iii. Not breastfeeding.

Participation of Women:

Pregnancy: The effects of mepolizumab on the developing human fetus are unknown. For this reason, women of childbearing potential must agree to use adequate contraception (see below for acceptable methods) prior to study entry, for the duration of study participation, and for >5 terminal half-lives (approximately 100 days) after administration of the last dose of study drug. Non-reproductive potential is defined as post-menopausal, male partner who has azoospermia or is surgically sterile (at least 6 weeks before screening) and is the sole sexual partner, surgical sterility, or a congenital or acquired condition that definitely prevents conception. Further, postmenopausal is defined as at least 12 consecutive months with no menses at age 50 or older, or a high follicle-stimulating hormone level in the postmenopausal range at ages 45-50 years in subjects not using hormonal contraception or hormone replacement therapy.

Females with reproductive potential must either practice complete and uninterrupted abstinence from heterosexual activity or use 2 of the following methods of contraception with their partners. The 2 methods must include either 2 barrier methods, or 1 barrier method and 1 non-barrier method, both of which must be consistently used:

Barrier Methods:

- 1) Diaphragm with spermicide
- 2) Cervical cap with spermicide or contraceptive sponge (for nulliparous subjects only)
- 3) Male or female condom (cannot be used together)

Non-Barrier Methods

- 1) An intrauterine device with a documented failure rate of <1%

- 2) Hormonal contraception: pill (estrogen/progestin or progestin-only), patch, vaginal ring, rod implanted in the skin, or subcutaneous injection methods

Females of childbearing-potential must have a negative pregnancy test result prior to receiving mepolizumab at each on-site study visit. During the course of the study, if a woman becomes pregnant or suspects she is pregnant, she should inform the study staff and her primary care physician immediately. Subjects who become pregnant will be entered into the mepolizumab pregnancy registry.

Fertility: There is no fertility data in humans. Animal studies showed no adverse effects of anti-IL-5 treatment on fertility.

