6.3.2 AEC nadir and mepolizumab administration (Visit 4)

Visit 4 will be scheduled to capture the AEC nadir. We anticipate that, for most subjects (assuming a 4-week cycle time), this will fall at about Day 15 (± 3 days). The schedule may be adjusted based on results of at-home CBCs.

The following procedures and laboratory tests will be performed:

- Targeted history and physical examination, including limb measurements
- Vital signs, including weight
- Review of symptom/weight logs and patient-reported outcome measures adherence
- CBC with differential
- Routine laboratory testing, including acute care panel, hepatic panel, mineral panel, LDH, CPK, CRP, and urinalysis
- Urine pregnancy test (females of childbearing potential only)
- Serum tryptase, aldolase, and quantitative immunoglobulin levels (including IgE)
- Collection of serum or plasma and urine for immunologic analyses and quantification of eosinophil granule proteins
- Collection of whole blood for storage of plasma and cells for research studies
- Whole blood lymphocyte phenotyping (TBNK) and RNAseq
- AE assessment

Following completion of the evaluations and pregnancy test (if applicable), mepolizumab 700 mg IV will be administered in the 5SW Day Hospital. The drug will be infused over about 30 minutes. Vitals will be checked and subjects will be able to leave 30 minutes after the infusion.

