6.4.2 Mepolizumab administration at 500 mg (Visits 9 and 10)

Visits 9 and 10 will be scheduled 28 days (± 7 days) from the prior visit. In-person visits are preferred, but these visits may be performed remotely if needed due to COVID-19 restrictions and difficulties with travel. In such cases, the pharmacy will provide autoinjectors for SC administration. Visit 10 should be performed at NIH if feasible.

The following procedures and laboratory tests will be performed:

- Targeted history and physical examination, including limb measurements. If the visit is conducted remotely, a targeted history and physical examination will be conducted virtually.
- Vital signs, including weight. The subject will measure and report their weight and temperature if the visit is performed remotely.
- Pregnancy test (females of childbearing potential; not performed at a remote visit)
- Review of symptom/weight logs and patient-reported outcome measures adherence

- CBC with differential
- Collection of serum or plasma and urine for immunologic analyses and quantification of eosinophil granule proteins (not performed at a remote visit)
- AE assessment
- Visit 10 only:
 - Routine laboratory testing, including acute care, hepatic, and mineral panels, LDH, CPK, CRP, and urinalysis (not performed at a remote visit)
 - Serum tryptase, and aldolase, serum immunoglobulins and IgE
 - Collection of whole blood for isolation and storage of plasma and cells for research studies (not performed at a remote visit)
 - Whole blood lymphocyte phenotyping (TBNK) (not performed at a remote visit) and RNAseq

Following completion of the evaluation and pregnancy testing (if applicable), mepolizumab 500 mg will be administered by IV infusion or by SC injection.

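### Section 4.3 defines postmenopausal in two conflicting ways and does not say which one decides who needs a pregnancy test before dosing

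*Combined protocol and SAP*

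**What the plan says.** Section 4.3, item 8(i), lists the women who count as being of non-childbearing potential: those with a hysterectomy or tubal ligation, and those who are "postmenopausal as defined by no menses in 1 year". It sets no age, FSH or hormone-use condition.

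The Participation of Women text in the same section defines the word again, in two limbs. The first reads "postmenopausal is defined as at least 12 consecutive months with no menses at age 50 or older". The second is an alternative that rests on FSH: "high follicle-stimulating hormone level in the postmenopausal range at ages 45-50 years in subjects not using hormonal contraception or hormone replacement therapy". This second definition serves a different term: "Non-reproductive potential is defined as post-menopausal, male partner who has azoospermia or is surgically sterile", followed by surgical sterility and congenital or acquired conditions that rule out conception.

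The safeguards are then attached to the two terms as follows.

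- Contraception: "Females with reproductive potential must either practice complete and uninterrupted abstinence from heterosexual activity" or use two methods.
- Testing: "Females of childbearing-potential must have a negative pregnancy test result prior to receiving mepolizumab at each on-site study visit".
- Visit lists in section 6, for example Visit 4: "Urine pregnancy test (females of childbearing potential only"; and Visits 9 and 10: "Pregnancy test (females of childbearing potential; not performed at a remote visit".
- The keys to Tables 1 and 2 in Appendix B also tie the test to child-bearing potential.

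**The concern.** Item 8(i) is the wider rule for amenorrhoea. A woman of 38 with a year of amenorrhoea from some cause other than menopause is exempt under it, and is not exempt under the later text. The test lines use the term that 8(i) addresses, so a site following the numbered criterion literally could dose her without a test.

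The later text leaves hormone users out of its FSH limb, so the protocol itself treats hormone use as relevant to classifying menopause. Item 8(i) has no such condition, although hormonal contraception is an allowed method. Section 8.1.2 lists menstrual irregularities among corticosteroid effects. It does not mention a year of amenorrhoea, so it shows only that the case is possible.

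What is at stake is fetal exposure. Section 4.3 says the effects of mepolizumab on the human fetus are unknown and makes a negative test a condition of on-site dosing. Sections 6.7 and 12.3 stop the drug in pregnancy, which depends on the pregnancy being detected. A woman without menses has no missed period to prompt a report.

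**Working it through.** No sample size, power or error rate is involved. The check compares the two definitions and then counts visits.

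**1. Definitions side by side** (exempt = counts as postmenopausal; the last column is the postmenopausal rule proposed under the fix)

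| Woman | Item 8(i) | Participation of Women | Proposed rule |
|---|---|---|---|
| 38, 12 months without menses | exempt | not exempt | not exempt |
| 47, 12 months, FSH not high | exempt | not exempt | not exempt |
| 47, 12 months, high FSH, off hormones | exempt | exempt | exempt |
| 47, menses within the year, high FSH, off hormones | not exempt | exempt if read literally | not exempt |
| 52, 12 months | exempt | exempt | exempt |

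The definitions disagree in 3 of the 5 profiles. The first two rows carry the concern. The fourth rests on reading the FSH limb as having no amenorrhoea condition, and the 12 months may have been meant for both limbs. If 8(i) governs testing she is tested, so the concern does not depend on this row. It matters only for drafting the fix.

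**2. Which term the tests use.** The pre-dose rule in 4.3, the test lines in section 6 and the Appendix B keys all say childbearing potential. The only explicit definition attached to that wording is the one for its opposite in 8(i).

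**3. Tests at issue for one affected woman**

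- Primary phase: tests at Visits 1, 4, 6 and 7 = 4. Those before a dose are at Visits 4, 6 and 7 = 3. Doses = 3.
- De-escalation, Visit 8: 4 + 1 = 5 tests; 3 + 1 = 4 pre-dose.
- Visits 9 to 13 add 0 if all are remote, since no subject is tested remotely, or 5 if all are on site. Range: 5 + 0 = 5 to 5 + 5 = 10 tests; 4 + 0 = 4 to 4 + 5 = 9 pre-dose.
- Doses with de-escalation: 3 + 6 (Visits 8 to 13) = 9.

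**4. Number of women.** Section 4.2 caps treated subjects at 12, and section 15.1 expects 5. The age and sex mix is not given, so the number affected cannot be estimated.

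**The case against.** The strongest reply is that the two terms are synonyms. The Pregnancy paragraph of 4.3 places the contraception duty on women of childbearing potential and points to the methods below. The text below imposes that duty on females with reproductive potential. The pre-dose test rule also sits in this part of the section, after the age and FSH definition, and not in item 8. On that reading the stricter definition governs and the 38-year-old is tested. This stands as a plausible reading, perhaps the intended one. It does not remove the conflict, because a numbered inclusion criterion then contradicts its own section with no rule on which prevails.

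The second reply is that the practical risk is small. The woman must be under 50 with a year of non-menopausal amenorrhoea and must conceive despite abstinence or two methods. Section 4.5 excludes pregnant women, section 4.3 asks for prompt self-report, and each dosing visit includes history, examination and AE assessment. The investigator may always test. All of this stands and sets the severity at low.

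Two stronger readings are tempting. A reader might infer that the protocol definitely exempts this woman from testing. The overlap of terms just described does not allow that. A reader might also infer that her contraception is waived. It is not: the two-method rule follows reproductive potential, whose definition of postmenopausal she does not meet.

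**Conclusion.** The conflict between the definitions is certain on the text. The missing test is one plausible consequence, arising where a site applies 8(i) literally to the test lines. In that case one woman would go without 4 required tests over 3 doses, or 5 to 10 over 9 doses with de-escalation. The conclusion assumes that a woman under 50 with non-menopausal amenorrhoea enrols; there may be none. Low severity: it is a wording fault with a possible safety effect, and it touches no endpoint, sample size or analysis.

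**What to change.** - In 8(i), define postmenopausal once: at least 12 consecutive months without menses, and either age 50 or older, or age 45-50 with a postmenopausal-range FSH off hormonal contraception and hormone replacement. Do not copy the present FSH limb unchanged; without the 12 months it would exempt women with recent menses.
- Move the other permanent categories (surgical sterility, and a congenital or acquired condition that definitely prevents conception) into 8(i). Otherwise a single term would leave them without a place.
- State that a sterile sole partner exempts a woman from contraception only, not from testing.
- Delete the second definition and use childbearing potential throughout 4.3, section 6 and Appendix B.

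The cost is a wording amendment, extended to the consent form if it repeats the definition, and at most a few urine tests at visits already held or an FSH test for a woman aged 45-50 who claims exemption.

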4.4 Subject Exclusion Criteria

A subject will not be eligible to participate in the study if any of the following conditions are fulfilled at the time of screening:

- 1) Treatment with immunosuppressive or immunomodulatory agents including but not limited to cyclosporine, interferon-alpha, azathioprine, methotrexate, and cyclophosphamide within the past 3 months.
- 2) Treatment with biologics including but not limited to mepolizumab, IVIG, anti-TNF agents, rituximab, benralizumab, alemtuzumab, reslizumab, dupilumab, lebrikizumab, and omalizumab within 6 months or 5 half-lives (whichever is longer). Subjects who received rituximab at any time in the past must have normal B-cell numbers to participate.
- 3) Co-morbid illness, alcohol or substance abuse, or any other condition (e.g., HIV, active hepatitis) that, in the opinion of the investigator, places the subject at undue risk by participating in the study.
- 4) Treatment with a daily dose of corticosteroids >40 mg.

Co-enrollment Guidelines: Co-enrollment in other trials is restricted, other than enrollment on observational studies or those evaluating the use of a licensed medication (see section 5.6). Study staff should be notified of co-enrollment as it may require the approval of the investigator.

4.5 Justification for Exclusion of Women, Minorities, Children, and Special Populations

Exclusion of Women:

- **Pregnancy:** Pregnant women are excluded from this study because the effects of mepolizumab on the developing human fetus are unknown (see section 4.3).

- **Breastfeeding:** Mepolizumab was excreted into the milk of cynomolgus monkeys at concentrations that were less than 0.5% of those detected in plasma. Because of the unknown but potential risk for adverse events (AEs) in nursing infants secondary to treatment of the mother with mepolizumab, subjects who are breastfeeding are not eligible for enrollment.

Exclusion of Children:

Although mepolizumab is approved for use in children 6 years and older with severe asthma and 12 years and older in HES, there is insufficient data in children with EAE to judge the potential risks. Moreover, the amount of blood required by this study exceeds the volume permitted for children; therefore, children are excluded from this study.

Exclusion of Decisionally Impaired Adults:

Adults who lack decision-making capacity to consent are not eligible for enrollment in this study (section 4.3), and an enrolled subject who permanently loses decision-making capacity to consent during the study will be withdrawn (section 12.8). NIH Policy 403 *Research with Subjects Lacking Capacity to Consent* will be followed.

5. Study Agent/Interventions

5.1 Disposition and Dispensation

Study agent will be distributed via the NIH Central Pharmacy according to standard pharmacy procedures.

5.2 Formulation, Packaging and Labeling

Study drug will be labeled with the drug name, dose, storage conditions, the name and address of the manufacturer, Investigational Use Statement (“Caution: New Drug – Limited by Federal [USA] Law to Investigational Use”) if investigational study agent is sent. For commercial agent labeled for subcutaneous use on the package, the agent may be reconstituted for IV use.

5.3 Study Agent Storage and Stability

Mepolizumab will be stored at temperatures of 2°C-8°C in the pharmacy and protected from light. Maintenance of a temperature log will be required to ensure no excursions.

5.4 Preparation, Administration, and Dosage of Study Agent

Study Agent: Mepolizumab 700 mg IV; 500 mg IV/SC; and 300 mg SC

Description

Mepolizumab is a fully humanized monoclonal antibody (IgG1, kappa mAb) supplied for IV infusion as 100 mg of lyophilized powder in sterile, single-dose vials. Mepolizumab for SC injection is supplied as single-dose prefilled autoinjectors containing 100 mg/mL mepolizumab as a clear to opalescent, colorless to pale yellow to pale brown solution.

Dosing and Administration

All subjects will receive mepolizumab 700 mg IV x 3 doses at approximately one-month intervals at study Visits 4, 6, and 7. Subjects in the Dose De-escalation Phase will receive additional monthly doses of 500 mg IV or SC at Visits 8 to 10, and 300 mg SC at Visits 11 to 13.

Dose Preparation

For the IV formulation: Mepolizumab 100 mg vials will be reconstituted with 1.2 mL sterile water for injection (according to the product labeling) and secondarily diluted in 100-250 mL of 0.9% normal saline (NaCl) for infusion (to a final concentration of 0.3-7.5 mg/mL). The reconstituted solution should be used as soon as possible but may be kept for up to 8 hours while refrigerated or at controlled room temperature (up to 25°C). Any unused solution remaining after 8 hours should be discarded.

For the SC formulation: Mepolizumab will be provided in prefilled autoinjectors each containing a single 100 mg/mL dose. The autoinjectors should be stored in the refrigerator and allowed to sit at room temperature for 30 minutes prior to injection. An autoinjector should not be used if it is dropped on a hard surface or if the solution appears cloudy, milky, or containing particular matter.

Route of Administration

For the IV formulation: Mepolizumab will be administered as a peripheral IV infusion over 30 minutes.

For the SC formulation: Mepolizumab administration will occur via an autoinjector and will be given by the subject or a caregiver as multiple injections of 100-mg each. Each injection should be given into the thigh or abdomen (avoiding the 5 cm [2 inches] around the navel) when given by the subject or caregiver; the upper arm may be used if the injection is administered by a caregiver. Each injection site should be separated by at least 5 cm (2 inches). Injections should not be administered into areas of skin that are tender, bruised, red, or hard. If a dose is missed, it should be administered as soon as possible. Thereafter, the subject should resume dosing on the usual day of administration. If the next dose is already due, then it should be administered as planned.

Dose Adjustments/Modifications/Delays

During the Primary Study Phase administering mepolizumab at 700 mg IV, the dose will remain the same without modification unless held or stopped due to a

pause (section 12.5), halt (section 12.6), or withdrawal of the subject (section 12.8). During the Dose De-escalation Phase, the dose will be reduced as outlined in the protocol unless held or stopped due to a pause, halt, or withdrawal of the subject.

Duration of Therapy

A total of 3 doses of 700 mg IV will be given on this protocol over a 3-month duration for all subjects; subjects in the Dose De-escalation Phase will have 6 months of additional de-escalating doses at 500 mg (3 doses) and 300 mg (3 doses). The total duration of therapy for participation in both the Primary Study Phase and the Dose De-escalation Phase will be 9 months.

Tracking of Dose

A record of the number of doses and lots used will be kept in the pharmacy for doses administered in-person at the NIH Clinical Center Day Hospital. For remote visits during the Dose De-escalation Phase, subjects will either have an observed administration via telehealth or will log the dose on a dose tracker.

Limitations on Prior Therapy

Subjects who have received mepolizumab within 6 months or 5 half-lives (whichever is longer) will not be eligible for this protocol.

Use of Ancillary Medications/Over-the-Counter Products/Foods

Only corticosteroids will be permitted for treatment in addition to mepolizumab. There are no restrictions on use of other prescribed medications, over-the-counter products or foods.

Subject Access to Study Agent After End of Study Assessments

All attempts to obtain approved mepolizumab will be pursued by the subject at the completion of the study.

